## 8.10. Exposure During Pregnancy

For both unapproved/unlicensed products and for marketed products, an exposure during pregnancy occurs if:

1. A female becomes, or is found to be, pregnant either while receiving or having been exposed (eg, because of treatment or environmental exposure) to the investigational product; or the female becomes, or is found to be pregnant after discontinuing and/or being exposed to the investigational product;

An example of environmental exposure would be a case involving direct contact with a Pfizer product in a pregnant woman (eg, a nurse reports that she is pregnant and has been exposed to chemotherapeutic products). 2. A male has been exposed (eg, because of treatment or environmental exposure) to the investigational product prior to or around the time of conception and/or is exposed during his partner's pregnancy.

If a study subject or study subject's partner becomes or is found to be pregnant during the study subject's treatment with the investigational product, the investigator must submit this information to the Pfizer Drug Safety Unit on a Serious Adverse Event (SAE) report form and an Exposure During Pregnancy (EDP) Supplemental Form, regardless of whether an SAE has occurred. In addition, the investigator must submit information regarding environmental exposure to a Pfizer product in a pregnant woman (eg, a subject reports that she is pregnant and has been exposed to a cytotoxic product by inhalation or spillage) using the EDP Supplemental Form. This must be done irrespective of whether an AE has occurred and within 24 hours of awareness of the exposure. The information submitted should include the anticipated date of delivery (see below for information related to termination of pregnancy).

Follow-up is conducted to obtain general information on the pregnancy and its outcome for all EDP reports with an unknown outcome. The investigator will follow the pregnancy until completion (or until pregnancy termination) and notify Pfizer of the outcome as a follow up to the initial EDP Supplemental Form. In the case of a live birth, the structural integrity of the neonate can be assessed at the time of birth. In the event of a termination, the reason(s) for termination should be specified and, if clinically possible, the structural integrity of the terminated fetus should be assessed by gross visual inspection (unless pre-procedure test findings are conclusive for a congenital anomaly and the findings are reported).

If the outcome of the pregnancy meets the criteria for an SAE (ie, ectopic pregnancy, spontaneous abortion, intrauterine fetal demise, neonatal death, or congenital anomaly [in a live born baby, a terminated fetus, an intrauterine fetal demise, or a neonatal death]), the investigator should follow the procedures for reporting SAEs.

Additional information about pregnancy outcomes that are reported as SAEs follows:

- Spontaneous abortion includes miscarriage and missed abortion.
- Neonatal deaths that occur within 1 month of birth should be reported, without regard to causality, as SAEs. In addition, infant deaths after 1 month should be reported as serious adverse events when the investigator assesses the infant death as related or possibly related to exposure to the investigational product

Additional information regarding the exposure during pregnancy may be requested by the investigator. Further follow-up of birth outcomes will be handled on a case-by-case basis (eg, follow-up on preterm infants to identify developmental delays). In the case of paternal exposure, the investigator will provide the study subject with the Pregnant Partner Release of Information Form to deliver to his partner. The Investigator must document in the source documents that the subject was given the Pregnant Partner Release of Information Form to provide to his partner.

### 8.10.1. Additional Postnatal Development Follow-up

The Investigator will be asked to assist with collection of assessments of postnatal development as part of a separate protocol. Participation in that protocol is optional and will require that the subject review, agree and sign a separate informed consent document specific to that study, explaining the details of the post-partum follow-up for the subject and the newborn to participate in these assessments of postnatal development.

## 8.11. Occupational Exposure

An occupational exposure occurs when during the performance of job duties, a person (whether a healthcare professional or otherwise) gets in unplanned direct contact with the product, which may or may not lead to the occurrence of an adverse event.

An occupational exposure is reported to the drug safety unit within 24 hours of the investigator's awareness, using the SAE report form, regardless of whether there is an associated AE/SAE. Since the information does not pertain to a subject enrolled in the study, the information is not reported on a Case Report Form (CRF), however a copy of the completed SAE report form is maintained in the investigator site file.

## 8.12. Withdrawal Due to Adverse Events (See Also Section 6.4 Subject Withdrawal)

Withdrawal due to AEs should be distinguished from withdrawal due to other causes according to the definition of AE noted earlier, and recorded on the appropriate AE CRF page.

When a subject withdraws because of an SAE, the SAE must be reported in accordance with the reporting requirements defined below.

## 8.13. Eliciting Adverse Event Information

The investigator is to report all directly observed AEs and all AEs spontaneously reported by the study subject. In addition, each study subject will be questioned about AEs.

## 8.14. Reporting Requirements

Each AE is to be assessed to determine if it meets the criteria for SAEs. If an SAE occurs, expedited reporting will follow local and international regulations, as appropriate.

## 8.14.1. Serious Adverse Event Reporting Requirements

If an SAE occurs, Pfizer is to be notified within 24 hours of investigator awareness of the event.

In particular, if the SAE is fatal or life-threatening, notification to Pfizer must be made immediately, irrespective of the extent of available AE information. This timeframe also applies to additional new information (follow-up) on previously forwarded SAE reports as well as to the initial and follow-up reporting of exposure during pregnancy, exposure via breastfeeding and occupational exposure cases.

In the rare event that the investigator does not become aware of the occurrence of an SAE immediately (eg, if an outpatient study subject initially seeks treatment elsewhere), the investigator is to report the event within 24 hours after learning of it and document the time of his or her first awareness of the AE.

For all SAEs, the investigator is obligated to pursue and provide information to Pfizer in accordance with the timeframes for reporting specified above. In addition, an investigator may be requested by Pfizer to obtain specific additional follow-up information in an expedited fashion. This information collected for SAEs is more detailed than that captured on the AE CRF. In general, this will include a description of the AE in sufficient detail to allow for a complete medical assessment of the case and independent determination of possible causality. Information on other possible causes of the event, such as concomitant medications, vaccines and/or illnesses must be provided. In the case of a subject death, a summary of available autopsy findings must be submitted as soon as possible to Pfizer or its designated representative.

#### 8.14.2. Non-Serious Adverse Event Reporting Requirements

All AEs will be reported on the AE page(s) of the CRF. It should be noted that the form for collection of SAE information is not the same as the AE CRF. Where the same data are collected, the forms must be completed in a consistent manner. For example, the same AE term should be used on both forms. AEs should be reported using concise medical terminology on the CRFs as well as on the form for collection of SAE information.

### 8.14.3. Medical Device Reporting Requirements

All medical device complaints regardless of whether the medical device complaint is associated with an AE will be collected on the applicable pages within the CRF. This includes potential incidents or malfunctions associated with the use of a medical device product. An incident or malfunction is an event that might have led to death or serious deterioration in health, or if it occurred again might have led to death or serious deterioration in health.

Pfizer is to be notified of all medical device complaints within 24 hours of the investigator's awareness of the event.

Refer to the Pharmacy Manual for procedures for forwarding medical device complaints not associated with an SAE to Pfizer.

### 8.14.4. Sponsor's Reporting Requirements to Regulatory Authorities

Adverse event reporting, including suspected unexpected serious adverse reactions, will be carried out in accordance with applicable local regulations.

## 9. DATA ANALYSIS/STATISTICAL METHODS

Detailed methodology for summary and statistical analyses of the data collected in this study will be documented in a Statistical Analysis Plan, which will be maintained by the sponsor. This document may modify the plans outlined in the protocol; however, any major

modifications of the primary endpoint definition and/or its analysis will also be reflected in a protocol amendment.

### 9.1. Sample Size Determination

A sample size of approximately 1000 subjects for each of the treatment groups of NSAID, tanezumab 2.5 mg and tanezumab 5 mg will be used in this study. This sample size allows for a high probability of observing subjects with any component of the composite endpoint where the event rate over this study is very small. If the event rate were 0.25%, then there would be a >90% probability of observing at least one subject with an event in any single treatment group.

In addition, the sample size allows for good precision to estimate the incidence rate for each treatment group in order to estimate an upper bound for the true incidence rate. The table below gives the width of the 95% confidence intervals for the individual treatment groups with this sample size.

Observed Rate of Rapidly Progressive Osteoarthritis Type 2	95% Confidence Interval for Individual Treatment Groups (N=1000)
0%	[0, 0.37%]
0.1%	[0.00, 0.56%]
0.2%	[0.02, 0.72%]
0.3%	[0.06, 0.87%]
0.4%	[0.11, 1.02%]
0.5%	[0.16, 1.16%]
1.0%	[0.48, 1.83%]

Table IV. Estimated Event Incidence Kate Precision	Table 10.	Estimated Event Incidence Rate Precision
--	-----------	---

For the assessment of the incidence of subjects with a total joint replacement, a sample size of approximately 1000 subjects per group would be sufficient to demonstrate a significant difference ( $p \le 0.05$ ) between any two treatment groups, for a difference of 2% with an observed control group rate for total joint replacement of 2%. Similarly, for the assessment of the incidence of subjects with an adjudication outcome of rapidly progressive osteoarthritis type 2, a sample size of approximately 1000 subjects per group would be sufficient to demonstrate a significant difference ( $p \le 0.10$ ) between any two treatment groups, for a difference of 1% with an observed control group rate for rapidly progressive osteoarthritis of 0%.

For the efficacy assessments, a sample size of approximately 1000 subjects per group gives 76% power for the treatment comparisons of both tanezumab 5 mg versus NSAID and tanezumab 2.5 mg versus NSAID all three co-primary efficacy endpoints, for assumed treatment differences of -0.73/-0.45 (tanezumab 5 mg/2.5 mg versus NSAID), -0.80/-0.53 and -0.21/-0.11 for WOMAC Pain subscale, WOMAC Physical Function subscale and the Patient's Global Assessment of Osteoarthritis, respectively. The within-group standard deviations were 2.73, 2.58 and 0.92 for WOMAC Pain subscale, WOMAC Physical Function subscale function subscale and Patient's Global Assessment of Osteoarthritis, respectively. The correlation of

the change from Baseline to Week 16 value for WOMAC Pain subscale versus WOMAC Physical Function subscale was 0.93. The correlations between Patient's Global Assessment of Osteoarthritis and WOMAC Pain and Physical Function subscales were approximately 0.68.

For the Japanese specific efficacy assessments, a sample size of 1000 subjects per group gives 95% power for the treatment comparisons of both tanezumab 5 mg versus NSAID and tanezumab 2.5 mg versus NSAID two co-primary efficacy endpoints, for assumed treatment differences of -0.73/-0.45 (tanezumab 5 mg/2.5 mg versus NSAID) and -0.80/-0.53 for WOMAC Pain subscale and WOMAC Physical Function subscale, respectively. The within-group standard deviations were 2.73 and 2.58 for WOMAC Pain subscale and WOMAC Physical Function subscale of Osteoarthritis, respectively. The correlation of the change from Baseline to Week 16 value for WOMAC Pain subscale versus WOMAC Physical Function subscale was 0.93.

A sample size of approximately 220 subjects per treatment group is required within each of the three NSAID cohorts (celecoxib, naproxen and diclofenac). This sample size would give an 80% power to detect statistical significance at the 5% significance level, for the comparison of tanezumab 5 mg versus individual NSAID groups in the WOMAC Pain subscale, assuming a treatment difference of -0.73 and a within-group standard deviation of 2.73.

Formal sample size calculation was not peformed for the actigraphy data collection, as published actigraphy data in a clinical trial with matched population was not available. However, data from Farr (2008), where the mean minutes of moderate to vigorous physical activity in an OA population is approximately 24 minutes per day, with a standard deviation of 20. Assuming a standard deviation for the change from Baseline of 14 (using a Baseline to post-Baseline correlation of 0.75 to represent strong association in activity over 2 timepoints), then a sample size of 120 subjects per treatment group would give 79 and 91% power for treatment differences of 5 and 6 minutes respectively (approximately 20 and 25% of the Baseline mean shown in this paper).

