# **3. STUDY DESIGN**

This is a randomized, double-blind, active-controlled, multicenter, parallel-group Phase 3 study of the safety and efficacy of tanezumab when administered by SC injection for 56 weeks compared to NSAIDs in subjects with osteoarthritis of the knee or hip. Approximately 3000 subjects will be randomized to one of 3 treatment groups in a 1:1:1 ratio (N=1000/treatment group). Treatment groups will include:

- SC placebo (to match tanezumab) once every 8 weeks (a total of 7 administrations) plus NSAID administered orally (PO) (naproxen 500 mg BID PO, celecoxib 100 mg BID PO, or diclofenac ER 75 mg BID PO) through Week 56.
- 2. Tanezumab 2.5 mg SC once every 8 weeks (a total of 7 administrations) plus placebo BID PO (to match naproxen, celecoxib or diclofenac ER) through Week 56.
- 3. Tanezumab 5 mg SC once every 8 weeks (a total of 7 administrations) plus placebo BID PO (to match naproxen, celecoxib or diclofenac ER) through Week 56.

Japan specific treatment groups are:

- 1. SC placebo (to match tanezumab) once every 8 weeks (a total of 7 administrations) plus celecoxib 100 mg BID administered orally (PO) through Week 56.
- 2. Tanezumab 2.5 mg SC once every 8 weeks (a total of 7 administrations) plus placebo BID PO to match celecoxib through Week 56.
- 3. Tanezumab 5 mg SC once every 8 weeks (a total of 7 administrations) plus placebo BID PO to match celecoxib through Week 56.

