# 7.3.9. Activity Level Monitoring (Actigraphy)

Subject activity level will be assessed using actigraphy in subjects at selected sites (to recruit a maximum of 360 subjects) in three separate monitoring periods. The monitoring periods will occur during the Screening period (Stage 2) and at approximately Weeks 16 and 56. During the Screening period, actigraphy over 7 consecutive days may take place anytime during the 2-week, pre-randomization NSAID regimen stabilization and prohibited drug washout periods and in parallel with the IPAP. Accelerometry to be completed prior to the Week 16 and Week 56 visits will take place over two separate, 14 consecutive day monitoring periods between Week 14 and the Week 16 visit and between Week 54 and the Week 56 visit, respectively.

Prior to each monitoring period, subjects will be instructed how to wear the accelerometer and to put the accelerometer on upon arising in the morning, and to wear the accelerometer continuously (except for water activities) until going to bed at night for 7 or 14 consecutive days (depending on the monitoring period) while going about their usual daily activities. Subjects will also be encouraged to maintain a log (electronic or written) to record when the accelerometer was put on in the morning and removed at night (or if removed for any other purpose).

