#### 9.2. Primary Analysis

### 9.2.1. Analysis of Primary Endpoints

The incidence of subjects with any of the adjudication outcomes of rapidly progressive osteoarthritis (type-1 or type-2), subchondral insufficiency fracture (or SPONK), primary osteonecrosis, or pathological fracture (primary composite endpoint) will be shown by number of subjects treated and subject years of exposure (treatment plus follow-up periods), for individual treatment groups and differences between tanezumab treatment groups and the NSAID treatment group. The risk ratio and risk difference with 95% confidence intervals will be calculated for the comparisons of each tanezumab treatment group versus the NSAID treatment group, as well as significance tests for each treatment comparison. The time to each event will be summarized, and (where there are sufficient numbers of subjects) Kaplan-Meier estimates of the time to event will be produced, together with an analysis of each tanezumab treatment group using the log-rank test.

The primary safety and efficacy population will be the ITT population, defined as all randomized subjects who received SC investigational product (either tanezumab or matching placebo). The primary efficacy analysis will use multiple imputation methods for missing data at Week 16. Details of the multiple imputation procedure are given below. All treatment comparisons will use the two-sided 5% significance level.

The co-primary efficacy endpoints will be analyzed using an ANCOVA model, with model terms for Baseline score, Baseline Diary Average Pain, index joint (hip or knee), Kellgren-Lawrence grade, NSAID cohort (diclofenac, celecoxib or naproxen) and treatment group, and study site as a random effect. The assessment of significance for the tanezumab SC versus NSAID treatment contrasts of the primary efficacy parameters will use a step-down testing strategy within each of the co-primary efficacy endpoints. This order of significance testing is defined as first testing tanezumab 5 mg versus NSAID, and if statistically significant ( $p \le 0.05$ ) to then test tanezumab 2.5 mg versus NSAID. Finally, the tanezumab dose group is declared as superior to NSAID if the corresponding treatment contrast is significant over all three co-primary endpoints (*two co-primary efficacy endpoints in Japan*). This testing procedure will maintain the Type I error to 5% or less within each of the co-primary efficacy endpoints (*two co-primary efficacy endpoints in Japan*).

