09001776e193181b656Approved\Approved On: 08-10-2019 08:56 (GMT)

11. Lower Extremity Activity Scale.

The LEAS is an 18-point scale ranging from 1 ('I am confined to bed all day') to 18 ('daily vigorous physical activity'), and is collected at Baseline and Weeks 4, 8, 16, 24, 56 and 80.

The number and percentage of subjects whose activity score is improved (increased), worsened (decreased) or have no change, and each level of change will be shown by treatment group for each week, using LOCF for any missing data. The mean (with standard deviation) and median change will also be summarized. The change from baseline to each post-Baseline visit (using LOCF for missing data), and for the worst change from Baseline (over all post-Baseline visits) will be summarized, and analyzed using CMH test (stratified by the combinations of the three stratification factors) (note, Week 80 data will be summarized, but not analyzed). If there are too few subjects in any stratification combination group (defined as <15 in any strata level) then the analysis will be modified to an unstratified test.

12. Accelerometry Endpoints.

The five accelerometry endpoints will be collected prior to Baseline (at least 4 days, with 1 being a weekend day) and prior to Weeks 16 and 56 (at least 8 days, with 2 being weekend days). The change from Baseline to Week 16 and 56 will be calculated for these parameters. Summaries and analyses of these endpoints will use observed data for change from Baseline to Weeks 16 and 56, and imputation using LOCF for Week 56.

These parameters will be analyzed using a negative binomial model using covariates of the corresponding Baseline accelerometry score, Baseline diary average pain, Index Joint, Highest KL grade (2, 3 or 4), NSAID cohort and Treatment.

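### The actigraphy power of 79% and 91% assumes that all of the roughly 360 recruited subjects give a change score; nothing is allowed for loss, and the observed-data Week 56 analysis is bound to lose subjects

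*Protocol*

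**What the plan says.** Protocol 9.1 introduces the actigraphy figures with a disclaimer: "Formal sample size calculation was not peformed for the actigraphy data collection". It then takes a mean of about 24 minutes per day of moderate to vigorous activity and an SD of 20 from a published study. From these it derives an SD of change ("Assuming a standard deviation for the change from Baseline of 14"), taking activity before and after treatment start to be correlated at 0.75, and concludes that "a sample size of 120 subjects per treatment group would give 79 and 91% power for treatment differences of 5 and 6 minutes". No visit is named, and no loss or non-evaluable share is mentioned.

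Protocol 7.3.9 sets the size of the subset: "to recruit a maximum of 360 subjects". Protocol 3 and 9.4.4.2 describe the same subset as approximately 360. Subjects are "randomized to one of 3 treatment groups in a 1:1:1 ratio".

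On the analysis, SAP 8.2.2 item 12 says: "Summaries and analyses of these endpoints will use observed data for change from Baseline to Weeks 16 and 56". The same sentence adds a last-observation-carried-forward (LOCF) analysis at Week 56, which has its own row in SAP 8.2.5. The model is negative binomial, with the Baseline accelerometry score as a covariate.

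**The concern.** A power statement is useful only if its n is the number that will be analysed. Here the n in the power statement equals the number recruited, so any loss lowers the power below what is printed.

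Some loss is built in. Follow-up devices go only to subjects who completed Baseline monitoring (Protocol 6.2.4.3 and 6.2.14.3). A complete follow-up period needs at least 8 valid days, including 2 weekend days (Protocol 9.4.4.2, SAP 6.3.4). The device for Week 56 is handed out at the Week 48 visit. A subject who fails the Week 16 pain-response rule or the Week 24 radiographic check has left the treatment schedule by then, and neither the Early Termination Schedule of Events nor the visit lists in Protocol 6.4.1 include actigraphy.

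Characterising changes in physical activity is a secondary objective, and Protocol 1.2.3.4.1 lists activity level among the variables to be related to joint safety events. A null Week 56 result read against a power of 79% to 91% would be more reassuring than the data warrant.

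**Working it through.** **Inputs.** From Protocol 9.1: n = 120 per group, SD 20, correlation 0.75, SD of change 14, differences of 5 and 6 minutes. The two-sided 5% level is stated for the primary analysis in Protocol 9.2.1 ("All treatment comparisons will use the two-sided 5% significance level"); I assume that it applies here.

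**SD of change.** 20 × √(2 × (1 − 0.75)) = 14.1, which the protocol rounds to 14.

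**Reproducing the plan.** Power = Φ(d / (SD × √(2/n)) − 1.96). With n = 120 and SD 14, the standard error is 14 × √(2/120) = 1.807.
- 5 minutes: 5/1.807 = 2.766; Φ(0.806) = 79.0%.
- 6 minutes: 6/1.807 = 3.320; Φ(1.360) = 91.3%.

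Both match. A one-sided test would give 86.9% and 95.3%, so the stated figures are two-sided. Solved for n, 79% at 5 minutes needs 120 per group and 91% at 6 minutes needs 119. The figure of 120 therefore contains no margin.

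**Recruited against needed.** 3 × 120 = 360, which is the entire subset.

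**Baseline adjustment.** The planned model includes Baseline activity. As a normal approximation, the residual SD is 20 × √(1 − 0.75²) = 13.23.

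**Power with loss.** The evaluable shares are assumptions.

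| Evaluable | n per group | SD 14: 5 / 6 min | Baseline-adjusted, SD 13.23: 5 / 6 min |
|---|---|---|---|
| 100% | 120 | 79.0% / 91.3% | 83.3% / 94.0% |
| 90% | 108 | 74.7% / 88.3% | 79.3% / 91.5% |
| 80% | 96 | 69.7% / 84.4% | 74.5% / 88.1% |
| 60% | 72 | 57.3% / 73.0% | 62.1% / 77.7% |

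**Is 60% at Week 56 far-fetched?** A rough check uses the protocol's own figures. Section 1.2.3.1 reports earlier studies with a mean Baseline WOMAC Pain above 7 and a typical reduction with tanezumab of 3 points or more. Section 9.1 gives a within-group SD of 2.73 and a difference of 0.73 between tanezumab 5 mg and NSAID. Take a Baseline of 7, so that a 30% reduction is 2.1 points, and a normal distribution:
- mean reduction 3: Φ((3 − 2.1)/2.73) = Φ(0.33) = 63%;
- mean reduction 3 − 0.73 = 2.27 (NSAID): Φ((2.27 − 2.1)/2.73) = Φ(0.06) = 52%.

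This covers only the Week 16 part of the response rule. It ignores the early-response condition, the Week 24 radiograph and other dropout. A larger mean reduction would raise the shares. It shows only that about 60% is within reason.

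**The case against.** The strongest reply is that the protocol promises nothing. It says that no formal calculation was made, gives an illustration on borrowed inputs, and gets the arithmetic right. That stands: there is no calculation error. But the illustration carries specific percentages, and its n equals the whole planned subset, so a reader will take it as the power of the substudy.

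A reader might infer that the design fails to deliver 79% and 91% at both visits. The documents do not support that for Week 16. Week 16 monitoring precedes the response decision, no loss rate is given, and Baseline adjustment could absorb about 10% loss (79.3% and 91.5% at 108 per group). Larger losses are not absorbed.

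The LOCF analysis at Week 56 keeps subjects with valid Week 16 data, so the Week 56 figures above apply to the observed-data analysis only. LOCF does so by putting Week 16 activity in place of Week 56 activity, and it does nothing for Week 16.

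Three further points stand in part. Only Protocol 7.3.9 makes 360 a ceiling; other sections say approximately. Neither document says outright that incomplete monitoring periods are dropped: SAP 5.4 admits subjects with any accelerometry data, and SAP 6.3.4 uses all valid data, so exclusion is a reasonable inference rather than a stated rule. And a negative binomial model reporting ratios was not what was powered, so the replacement figures are approximations too.

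**Conclusion.** The point holds in a limited form. The printed power is correct for 120 analysed subjects per group, but no allowance is made for loss. For the observed-data analysis at Week 56 it is too high as written, because the schedule leaves discontinued subjects without actigraphy. At an assumed 60% evaluable, power is about 57% and 73% unadjusted, or 62% and 78% with Baseline adjustment under a normal approximation. For Week 16 the direction is clear but the size is not: the shortfall could be negligible at 10% loss or less with adjustment, and is about 9 and 7 points unadjusted at 20% loss. All of this rests on assumed evaluable shares, equal loss across groups, and a comparison of means in place of the planned model. The point is minor; it affects how a secondary activity result is read and nothing in the primary conclusions.

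**What to change.** In Protocol 9.1:
- State that 79% and 91% assume 120 evaluable subjects per group.
- Give the expected evaluable number per group at Week 16 and at Week 56, with the power at each. If the shares remain assumptions, label them and show a range such as the table above.
- Say that the calculation is for a difference in mean change, whereas the planned analysis is negative binomial with a Baseline covariate.
- Note that the Week 56 LOCF analysis retains subjects with valid Week 16 data, and that the lower Week 56 power refers to observed data.

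Reconcile the ceiling of 360 in Protocol 7.3.9 with the approximate 360 in Protocol 3 and 9.4.4.2. State in SAP 6.3.4 whether incomplete monitoring periods are excluded.

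Confidence intervals for the activity ratios are already planned in Protocol 9.4.4.2, so no change is needed there. The cost is a less favourable printed figure; no extra patients or procedures are required.
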